6.0 ANALYSIS POPULATIONS

6.1 Enrolled Population

The enrolled population is defined as all patients who enrolled in the study.

6.2 Safety Population

The safety population will include all enrolled patients who receive at least 1 dose of SD-101 (Protocol section 12.4). The primary analysis population for the study will include the safety population with separate analyses for Phase 1 Dose Escalation and each Phase 2 Dose Expansion analysis group.

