4.1.3 Phase 2 Dose Expansion – Dosing Schedule

As presented in the Trial Flow Diagrams for the Dose Expansion Cohorts 1 to 4, patients with metastatic melanoma or HNSCC will receive 2 courses of the SD-101 dose regimen, with 9 weeks off between the 2 courses. In Cohorts 1 and 3 ([Figure 4-3](#)), patients will have a lead-in dose of pembrolizumab at Day 1 and start the treatment course on Day 22; whereas, in Cohorts 2 and 4 ([Figure 4-4](#)), SD-101 and pembrolizumab treatments will both start on Day 1. Metastatic melanoma or HNSCC patients in Cohorts 5, 6, 7, and 8 ([Figure 4-5](#)) will receive 1 course of SD-101 and dosing with SD-101 and pembrolizumab both start on Day 1. Pembrolizumab 200 mg will be administered intravenously Q3W until disease progression or up to 2 years. SD-101 will be administered before pembrolizumab on days when both drugs are scheduled to be used.

Figure 4-3: Trial Flow Diagram for Dose Expansion Cohorts 1 and 3 (CLOSED)

[figure not shown]

Figure 4-4: Trial Flow Diagram for Dose Expansion Cohorts 2 and 4 (CLOSED)

[figure not shown]
[figure not shown]

Figure 4-5: Trial Flow Diagram for Dose Expansion Cohorts 5, 6, 7, and 8 (CLOSED)

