5.3 Removal of Patients From the Trial

Patients may choose to withdraw from the trial at any time. The reason for withdrawal will be recorded on the case report form (CRF).

Patients may also be discontinued from the trial by the investigator for any of the following reasons:

- Patient does not receive the first dose of SD-101
- Pembrolizumab is discontinued because of toxicity
- Patient begins new cancer treatment for melanoma or HNSCC (as applicable)
- Noncompliance with trial procedures as determined by the investigator or sponsor
- At the discretion of the investigator if it is felt to no longer be in the best interest of the patient to remain in the trial
- If patient becomes pregnant and/or starts breastfeeding
- The sponsor decides to terminate the trial

The investigator or designee should discuss with the Dynavax Medical Monitor prior to withdrawing a patient from the trial before trial completion. When a patient discontinues the trial, they should undergo an EOS/Safety Follow-up Visit 28 days after the last dose of trial treatment as described in Section 10.8. Required procedures are listed in [Appendix 1](#) through [Appendix 4](#). Additional information about stopping treatment or terminating the trial may be found in Sections [7.6](#), [9.1](#) and [9.2](#).

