6.0 TRIAL TREATMENT AND SUPPLIES

The identities and instructions for administration, storage, and handling of SD-101 and pembrolizumab are described below. Both SD-101 and pembrolizumab are considered as, and referred to as, trial drug(s) or trial treatment in this protocol.

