12.4 Trial Analysis Populations

The safety population will include all enrolled patients who receive at least 1 dose of both pembrolizumab and SD-101. The primary analysis population for the study will include the safety population with separate analyses for Phase 1 Dose Escalation and each Phase 2 Dose Expansion cohort. The efficacy population will comprise all patients who receive at least 1 dose of both pembrolizumab and SD-101 and who have baseline and at least 1 post-baseline imaging assessment. The ITT population will include all enrolled subjects regardless of having a post-baseline radiographic assessment. Additional subpopulations for an exploratory and retrospective analysis may include PD-L1 status (positive or negative [ie, < 1% positivity]) and specific prior anti-PD-1/PD-L1 therapy. Further details of statistical considerations will be provided in a separate Statistical Analysis Plan.

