12.7 Safety Analyses

All safety data will be analyzed descriptively and will be based on the all-treated population. The most important safety parameters will be presented for all sites combined. Summary statistics will be used to describe the incidence of all injection-site reactions, AEs, SAEs, deaths, and laboratory values. DLTs occurring in Phase 1 will be summarized by dose level received and presented in both tables and listings.

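### The protocol and SAP safety populations leave out Cohort 1 and 3 patients who received only lead-in pembrolizumab, while the protocol bases safety summaries on an undefined all-treated population

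*SAP*

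**What the plan says.** The two documents describe the safety analysis set in three ways.

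- SAP 6.2 takes "all enrolled patients who receive at least 1 dose of SD-101" and cites Protocol 12.4 as its source. SAP 9.7 uses this set for the safety analyses.
- Protocol 12.4 takes "all enrolled patients who receive at least 1 dose of both pembrolizumab and SD-101" and makes this the primary analysis population.
- Protocol 12.7 says that the safety analyses "will be based on the all-treated population". The synopsis uses the same term after its Phase 1 paragraph, and Protocol 12.5 uses it for baseline characteristics. It is not among the populations set out in Protocol 12.4 or SAP 6.

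On what counts as treatment, Protocol 6.0 is explicit: "Both SD-101 and pembrolizumab are considered as, and referred to as, trial drug(s) or trial treatment in this protocol". Protocol 5.1 treats a patient as enrolled at the first dose of either drug.

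In Cohorts 1 and 3, according to Protocol 4.1.3, "patients will have a lead-in dose of pembrolizumab at Day 1 and start the treatment course on Day 22". Protocol 5.3 allows for patients who do not get that far. One listed reason for removal from the trial is "Patient does not receive the first dose of SD-101". Protocol 7.8 lets Phase 2 patients without a dose of both drugs be replaced.

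**The concern.** A safety population should normally depend only on having been treated. Here, for Cohorts 1 and 3, membership depends on still being on study three weeks after treatment began, and that can be affected by the first dose itself. Protocol 7.7 notes that immune-related events can appear soon after the first pembrolizumab dose.

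If such an event, or a death, kept a patient from the first SD-101 injection, it would be missing from the summaries of treatment-emergent events, serious events, discontinuations and deaths in SAP 9.7.3. The denominator would shrink as well.

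The rule also works unevenly within a table. In the anti-PD-1/L1 naïve groups, Cohorts 1 and 3 have the lead-in, while Cohorts 5 and 6 start both drugs on Day 1.

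**Working it through.** **Step 1: one patient against each rule.** Take a patient in Cohort 1 or 3 who receives pembrolizumab on Day 1 and stops before Day 22.

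| Source | Rule | Status of this patient |
|---|---|---|
| Protocol 5.1 | Enrolled at first dose of either drug | Enrolled |
| Protocol 6.0 | Both drugs are trial treatment | Treated |
| Protocol 10.3.9 | Adverse events evaluated from the first trial treatment on Day 1 | Under collection |
| Protocol 12.7, synopsis | All-treated population (undefined) | In, on the plain meaning |
| Protocol 12.4 | Both drugs | Out |
| SAP 6.2 | SD-101 | Out |
| SAP 9.7 | Safety population of SAP 6.2 | Out of the safety summaries |

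**Step 2: the same event in two patients.** SAP 7.1 starts the treatment-emergent period at the first dose of study drug. Read with Protocol 6.0, that is the Day 1 pembrolizumab dose. Suppose two patients have the same event on Day 10. One recovers and is injected on Day 22, and the event is tabulated. The other stops because of the event, and it is not tabulated. Inclusion turns on what happened after treatment started.

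**Step 3: patients who pass through the window.** The planned sizes in Protocol 4.1 are about 60 (Cohort 1) and about 25 (Cohort 3).

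- Planned lead-in patients: N = 60 + 25 = 85.
- Share of planned Phase 2: 85 / (160 + 100) = 85 / 260 = 33%.
- Time on pembrolizumab alone: Day 22 − Day 1 = 21 days.

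**Step 4: possible size (illustration only).** The documents give no count of patients who stopped before Day 22, so the loss d is assumed. Excluded patients are k = N × d. If every excluded patient had the event and the rate in the rest is r, the summary understates the proportion in all N by [r(N − k) + k]/N − r = k(1 − r)/N. This is the upper limit for a given k and r.

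| Assumed d | 85 × d | k (rounded) | Understatement, r = 10% | Understatement, r = 20% |
|---|---|---|---|---|
| 0% | 0 | 0 | 0 | 0 |
| 1% | 0.85 | 1 | 1 × 0.9/85 = 1.1 points | 0.9 points |
| 2% | 1.7 | 2 | 2 × 0.9/85 = 2.1 points | 1.9 points |
| 5% | 4.25 | 4 | 4 × 0.9/85 = 4.2 points | 3.8 points |
| 10% | 8.5 | 9 | 9 × 0.9/85 = 9.5 points | 8.5 points |

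The SAP reports by group rather than pooled, so a single exclusion can weigh more. One such patient among the 25 of Cohort 3, with r = 10%, gives 1 × 0.9/25 = 3.6 points.

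The plan states no figure on this point, so there is none to reproduce.

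**The case against.** The strongest reply is that the restriction has a purpose. The Phase 2 safety objective concerns SD-101 combined with pembrolizumab, and a patient given one pembrolizumab dose never received the combination. The replacement rule in Protocol 7.8 follows the same logic. This supports showing SD-101-exposed patients separately. It does not support leaving treated patients out of every safety summary when Protocol 12.7 asks for all treated patients.

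Four stronger readings are tempting, and the documents do not support them.

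- *The SAP breaks a clear protocol rule.* The all-treated term is undefined and may have been meant as a loose name for the set in Protocol 12.4. For lead-in-only patients the SAP agrees with 12.4. The conflict rests on the plain meaning of the term, read with Protocol 5.1 and 6.0, and it lies inside the protocol as much as between the documents.
- *These patients vanish from the report.* They stay in disposition, with reasons for discontinuation (SAP 9.1), and in intent-to-treat demographics (SAP 9.3). SAP 9.7.3 promises listings of all treatment-emergent events, although SAP 9.7 may confine these to the safety population. The Phase 1 dose-limiting toxicity tables are unaffected because both drugs start on Day 1 there.
- *The excluded patients are mainly those with early toxicity.* Protocol 5.3 does not tie a missed first SD-101 dose to toxicity. Withdrawal, noncompliance or new cancer treatment are other routes. Progression of the study cancer is not an adverse event under Protocol 11.2.
- *The differing SAP and protocol wording changes who is counted here.* Pembrolizumab comes first in Cohorts 1 and 3, so both definitions select the same lead-in patients. They differ only for someone given SD-101 but never pembrolizumab.

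**Conclusion.** The point stands in limited form. Protocol 12.7 and the synopsis name a safety set that is never defined. The sets that are defined, in Protocol 12.4 and SAP 6.2, exclude patients who are enrolled, treated and under adverse event collection. For about 85 planned patients, an event in the first 21 days enters the safety summaries only if the patient reaches SD-101.

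The numerical effect is unknown. It is nil if nobody stopped before Day 22. The illustrated understatement of about 1 to 4 points at 1% to 5% loss rests on an assumed loss, on planned rather than actual enrolment, and on every excluded patient having had the event. A reader might infer that reported safety is in fact understated. The documents show that the rule permits this, not that it happened.

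The definition should still be settled before the final tables. It is a small correction, and safety is the Phase 2 endpoint still being collected after Amendment 9.

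**What to change.** 1. In Protocol 12.4 and SAP 6.2, define the safety population as all patients who receive at least one dose of either trial drug. State that this is the all-treated population of Protocol 12.7, 12.5 and the synopsis, and use it throughout SAP 9.7.
2. The SAP 9.11 tables are split by 2 mg and 8 mg, and a patient who was never injected has no SD-101 dose and fits under neither. Show lead-in-only patients in a separate column or row within their tumor and anti-PD-1/L1 group (MEL/NAIVE for Cohort 1, HNSCC/NAIVE for Cohort 3), and count them in the group total.
3. Keep patients given at least one SD-101 dose as a labelled subset for the by-dose tables. This serves the combination-safety objective.
4. State the number of lead-in-only patients in the disposition table, including when it is zero.

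No new data are needed, because adverse events are already collected from Day 1. The cost is a wording change in two sections, an added column or row in the two affected groups (with a group total where the table shells lack one), and possibly slightly higher reported event rates.

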6.3 Efficacy Population

The evaluable population will comprise all patients who receive at least 1 dose of both pembrolizumab and SD-101 and who have baseline and at least 1 post-baseline imaging assessment. The ITT population will include all enrolled subjects regardless of having a post-baseline radiographic assessment. Additional subpopulations for an exploratory and

retrospective analysis may include baseline PD-L1 status (positive or negative [ie, < 1% positivity]) and specific prior anti-PD-1/PD-L1 therapy (Protocol section 12.4).

Prior anti-PD-1/PD-L1 therapy subpopulations are reflected in the study groups. Analyses will be performed according to the dose groups in Phase 1 and study groups in Phase 2 for evaluable and ITT population.

6.4 Pharmacodynamic Population

The pharmacodynamic population will include all enrolled patients who receive at least 1 dose of SD-101 and who have screening and at least 1 post-baseline assessment of INF-alpha inducible gene expression.

7.0 DEFINITIONS, COMPUTATIONS, AND CONVENTIONS

7.1 Definitions and Computations

Study Day

Study day will be calculated in reference to the date of first dose (Day 1). For assessments conducted on or after the first dose date, study day is calculated as (assessment date – first dose date + 1). For assessments conducted before the first dose date, study day is calculated as (assessment date – first dose date). There will be no Day 0.

Date of First Dose and Date of Last Dose of Study Drug

The date of the first dose of study drug is defined as the date a patient receives the first dose of the study drug. The date of the last dose of study drug is the date a patient receives the last dose of the study drug.

Treatment-Emergent Period

Treatment-emergent periods are updated from what were described in the protocol (sections 10.3.9 and 10.3.10) to cover the maximum possible reporting periods.

Treatment-emergent period for AEs is defined the date and time of the first dose of study drug administration through 90 days after last dose of study drug administration.

Treatment-emergent period for SAEs is defined as the date and time of the first dose of study drug administration through EOS.

Baseline Value and Post-baseline Value

Unless otherwise specified, the baseline value is defined as the last measurement before the first dose (date and time) of study drug. Post-baseline value is defined as a measurement taken after the first dose of study drug. Change from baseline is defined as (post-baseline value – baseline value). Both date and time of study drug administration and measurement

will be considered when calculating baseline value. If time is not available, then date only will be used.

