4.7 Trial Termination

The End-of-Study (EOS) date is defined as the date of the last visit of the last participant. However, the sponsor reserves the right to terminate the trial at any time. Reasons for discontinuation include but are not limited to:

- Inability to enroll sufficient patients into the trial
- Good clinical practices (GCP) compliance issues that compromise the validity of the trial

Procedures for withdrawal of individual patients can be found in Section 5.3.

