10.3.10 Serious Adverse Events

All SAEs, as defined in Section [11.3.1](#), will be evaluated from the time the consent is signed through 90 days following cessation of trial treatment or EOS (whichever is later), or 28 days following cessation of trial treatment if the patient initiates new anti-cancer therapy. Any SAE must be reported to Dynavax or its designee within 24 hours of the knowledge of the event.

An SAE, whether assessed as related or not related to study treatment, will be followed until considered stable, resolved, or until EOS, or the patient initiates new anti-cancer therapy (whichever is earlier).

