11.3.2 Serious Adverse Event Reporting Requirements

Any SAE that occurs from the time the consent is signed through 90 days following cessation of trial treatment or EOS (whichever is later), or 28 days following cessation of trial treatment if the patient initiates new anti-cancer therapy, whether or not the SAE is related to the trial treatment (SD-101 and/or pembrolizumab), **must be reported to Dynavax or its designee within 24 hours of investigator awareness of the event.** The contact information for reporting SAEs is provided in the Study Reference Manual. General SAE reporting instructions are as follows:

- Submit SAE documents according to instructions in the Study Reference Manual.
- Record all SAEs on the AE CRF.
- For SAEs, record the primary event on the AE CRF; describe events occurring secondary to that primary event on the SAE form in the narrative description of the case.
- Death is an outcome, not an event. Record the event that resulted in the death as the fatal event on the AE CRF.
- For hospitalizations for surgical or diagnostic procedures, record the illness leading to the surgical or diagnostic procedure as the SAE, not the procedure itself. Capture the procedure in the narrative as part of the action taken in response to the illness.
- Elective hospitalizations will not be considered SAEs and do not need to be reported. Complications that prolong elective hospitalizations should be recorded as SAEs. Emergency room visits of less than 24 hours do not meet the criterion of hospitalization for SAE reporting purposes.

The SAE report should contain, at a minimum, the following information:

- Patient identifiers (ie, patient number)
- Suspected medicinal product
- AE term (must be listed as serious)
- Contact information for person reporting event

The relationship of the SAE to trial treatment will be assessed by the investigator (Section 11.4.2). Follow-up information should be actively sought and submitted as it becomes available.

The investigator will assess relationship to trial treatment. In addition, the sponsor will assess relationship to trial treatment and determine expectedness to SD-101 based on the current SD-101 Investigator's Brochure and to pembrolizumab based on the pembrolizumab Investigator's Brochure. The sponsor will report all SD-101 suspected and unexpected serious

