NOTE: As of Amendment 9, Phase 2 of the trial has been modified to continue dosing per protocol; however, efficacy and exploratory endpoints will no longer be collected, and the collection of safety endpoints has been simplified. The final study visit will be the EOS/Safety Follow-up. All other procedures to monitor disease progression and safety should be performed at the investigator's discretion according to local standard of care; these data do not need to be collected on the CRE. This Schedule of Trial Events has been amended and assessments that are no longer required have been deleted.

Screening Through Day 358

Trial Period:	Screening	Trial Treatment																						
		(every week ± 1 day)					(every 3 weeks ± 3 days)					(every 3 weeks ± 3 days)												
Day:	-28 to -1 ^a	1	8	9 ^{b,cc}	15	22	29	43	64	85	106	127	148	169	190	211	232	253	274	295	316	337	358	
Study Procedures																								
Informed consent	X																							
Inclusion/Exclusion Criteria	X																							
Demographics/Medical history/Prior medications ^g	X	X																						
Vital signs ^h	X	As of Amendment 9, per local standard of care at the discretion of the investigator.																						
Physical examination ⁱ	X																							
ECOG Performance Status	X																							
12-Lead ECG ^j	X																							
Review AEs ^k		X	X	X	X	X		X	X	X	X	X	X	X	X	X	X	X	X	X	X	X	X	
Review SAEs	X	X	X	X	X	X		X	X	X	X	X	X	X	X	X	X	X	X	X	X	X	X	
Concomitant medications ^l	X	X	X	X	X	X		X	X	X	X	X	X	X	X	X	X	X	X	X	X	X	X	
HIV, HPV status, and hepatitis testing ^m	X																							

APPENDIX 4: SCHEDULE OF TRIAL EVENTS (PHASE 2 EXPANSION COHORTS 5 AND 6 [ANTI-PD-1/L1 NAÏVE] AND COHORTS 7 AND 8 [ANTI-PD-1/L1 REFRACTORY OR RESISTANT]) (CLOSED) (CONT'D)

Screening Through Day 358 (Cont'd)

Trial Period:	Screening	Trial Treatment																					
		(every week ± 1 day)					(every 3 weeks ± 3 days)					(every 3 weeks ± 3 days)											
Day:	-28 to -1 ^a	1	8	9 ^{b, ee}	15	22	29	43	64	85	106	127	148	169	190	211	232	253	274	295	316	337	358
Serum chemistry and CRP ⁿ	X	X	X		X	X		X	X	X	X	X	X	X	X	X	X	X	X	X	X	X	X
Hematology ^o	X	As of Amendment 9, per local standard of care at the discretion of the investigator.																					
Coagulation ^p	X																						
Thyroid function tests ^q	X																						
Urinalysis with microscopy																							
Pregnancy testing ^r	X																						

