APPENDIX 1-4 FOOTNOTES

AE = adverse event; ALT = alanine transaminase; ANC = absolute neutrophil count; aPTT = activated partial thromboplastin time; AST = aspartate transaminase; BUN = blood urea nitrogen; CBC = complete blood count; Cr = creatinine; CRP = C-reactive protein; CT = computed tomography; D = Day; DLT = dose-limiting toxicity; ECG = electrocardiogram; ECOG = Eastern Cooperative Oncology Group; eCRF = electronic case report form; EOS = End-of-Study; F/U = follow-up; Hgb = hemoglobin; HIV = human immunodeficiency virus; IFN = interferon; LDH = lactate dehydrogenase; MRI = magnetic resonance imaging; NCI CTCAE = National Cancer Institute Common Terminology Criteria for Adverse Events; PD = progressive disease; PD-1 = programmed death receptor-1; PD-L1 = programmed death-ligand 1; PT = prothrombin time; Q3W = every 3 weeks; RECIST = Response Evaluation Criteria In Solid Tumors; RNA = ribonucleic acid; SAE = serious adverse event; TSH = thyroid stimulating hormone; UNS = unscheduled visit/Safety Follow-up Visit; WBC = white blood cell; WOCBP = women of childbearing potential.

Screening ^a	Routine laboratory tests (serum chemistry, hematology) for screening should be performed within 28 days prior to enrollment or can be obtained from a standard of care visit within 28 days of first dose of pembrolizumab. Laboratories obtained within 7 days of Day 1 visit, with the exception of a CBC with ANC, do not need to be repeated on Day 1.
24-hour postdose visit ^b	The window for 24-hour postdose visit is ± 3 hours.
DLT Assessment Period ^c	DLT assessment period is Study Day 1 through Study Day 29.
Extended Pembrolizumab Treatment ^d	During Extended Pembrolizumab Treatment, pembrolizumab will be administered Q3W with standard of care procedures performed by the site. Data related to dosing, concomitant medications, AEs, and SAEs must be entered in the CRF.
EOS / Safety FU ^e	After a patient is discontinued from both trial treatments, a mandatory EOS/Safety Follow-up visit will be performed 28 (± 3) days after the last administration of trial treatment, regardless of the reason for permanent discontinuation.

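### SAP 7.1 ends the SAE treatment-emergent window at EOS without the 90-day limb, so as written it can be shorter than the SAP's own 90-day AE window

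*SAP*

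**What the plan says.** SAP 7.1 replaces the periods in Protocol 10.3.9 and 10.3.10 and gives its reason: "to cover the maximum possible reporting periods". It then sets two windows, both starting at first dose.

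- AEs run "through 90 days after last dose of study drug administration".
- SAEs: "Treatment-emergent period for SAEs is defined as the date and time of the first dose of study drug administration through EOS".

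Protocol 10.3.10 follows SAEs "through 90 days following cessation of trial treatment or EOS (whichever is later", or to 28 days after treatment stops if new anti-cancer therapy is started. Protocol 11.3.2 sets the same reporting period: "Any SAE that occurs from the time the consent is signed through 90 days following cessation of trial treatment or EOS (whichever is later". Protocol 10.3.9 and 11.2 collect non-serious AEs only to 28 days after last dose.

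EOS has two meanings. The SAP abbreviation list gives it as the End-of-Study visit, and the footnotes to Protocol Appendices 1 to 4 time that visit: "a mandatory EOS/Safety Follow-up visit will be performed 28 (± 3) days after the last administration of trial treatment". Protocol 4.7 gives a trial-level meaning, in which the EOS "date is defined as the date of the last visit of the last participant". SAP 7.1 does not say which it intends.

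SAP 9.7.3 counts an event as a TEAE if it begins or worsens in the treatment-emergent period. SAP 7.3 compares partial dates with the end of that period. Both sections speak of one period, although 7.1 has defined two.

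**The concern.** A window meant to cover the longest reporting period needs both limbs of the protocol rule. The SAP keeps EOS, drops the 90 days for serious events, and attaches the 90 days to AEs.

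The gap falls where the late serious events are. Because the protocol stops collecting non-serious AEs 28 days after last dose, events recorded after that are almost all serious. If the SAE sentence is applied to the serious tables, an SAE on day 60 could be counted in the overall TEAE tables and left out of the serious-TEAE table, or out of the table of TEAEs leading to death. The tables would then disagree about the same event.

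Late events are plausible. Protocol 7.7 warns that immune-related events can appear months after the last pembrolizumab dose. Protocol 2.6 reports a hypophysitis 85 days after last treatment in Phase 1 (its seriousness is not stated). AE and SAE incidence is a Phase 1 primary endpoint. Together with injection-site reactions, it is the only Phase 2 endpoint still collected after Amendment 9, so consistent serious-event counts matter to the final report.

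**Working it through.** The SAP gives no day count for the SAE window, so there is no stated figure to reproduce. The check is window arithmetic in days after last dose, taking last dose as the final dose of either trial drug.

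**Inputs**
- AE window end: day 90 (SAP 7.1).
- EOS visit: day 28, range 25 to 31 (footnotes to Protocol Appendices 1 to 4).
- Trial-level EOS: the date of Protocol 4.7.
- Protocol SAE period: the later of day 90 and EOS (10.3.10, 11.3.2).

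**EOS as the patient's own visit.** Gap = 90 − visit day.
- On schedule: 90 − 28 = 62 days.
- Latest visit: 90 − 31 = 59 days. Earliest visit: 90 − 25 = 65 days.
- Example: with a last pembrolizumab dose on Day 715, the SAE window ends on Day 715 + 28 = 743 and the AE window on Day 715 + 90 = 805, a difference of 62 days.

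This applies to every patient with an on-schedule visit. On this reading the protocol's choice of the later date would always give 90 days, since 31 < 90, and its EOS limb would do nothing. That favours the trial-level meaning in the protocol. The SAP's abbreviation list still points to the visit.

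**EOS as the trial-level date.** The notes to Protocol Appendices 2 to 4 say: "The final study visit will be the EOS/Safety Follow-up". Assume that the last participant's last visit is this visit, on schedule, after the last dose in the trial. For a patient last dosed d days before that dose, EOS falls g = d + 28 days after the patient's own last dose. Gap = max(0, 90 − g) = max(0, 62 − d), with 59 to 65 in place of 62 for the ± 3-day visit window.

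| d (days) | SAE window ends (day) | Gap to day 90 | Gap with ± 3 days |
|---|---|---|---|
| 0 (last patient out) | 28 | 62 | 59 to 65 |
| 21 | 49 | 41 | 38 to 44 |
| 42 | 70 | 20 | 17 to 23 |
| 63 | 91 | 0 | 0 to 2 |

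Since 62 / 21 = 2.95, the gap affects patients last dosed within about three 3-week cycles of the end of dosing, and always the last patient out. Everyone else has an SAE window of at least 90 days.

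**With both limbs.** The window ends at max(90, EOS), which is at least 90 under either meaning, so it is never shorter than the AE window.

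**The case against.** The strongest reply is that the two sentences work together. With non-serious AEs collected only to day 28, the 90-day AE window can matter after that almost only for serious events. Read jointly, the sentences give 90 days, extended to EOS for SAEs, which is close to the protocol rule and fits the stated aim. An SAE is an AE (Protocol 11.3.1), and SAP 9.7.3 tabulates serious TEAEs, which can be read as the serious subset of all TEAEs. A day-60 SAE is then already a serious TEAE. SAP 7.3 also treats doubtful cases as treatment-emergent.

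Much of this stands. A reader might infer that the SAP will drop serious events or undercount them. The documents do not support that: a reasonable programmer could apply the 90-day window and lose nothing. A reader might also want a count of affected patients. It would need the distribution of last-dose dates, which the documents do not give; cohorts opened and closed at different amendments, so an even spread cannot be assumed. Nor can one say that the SAP departs from its own source protocol, because it cites Amendment 8 and only the Amendment 9 text is available.

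The reply does not remove the problem. SAP 7.1 gives SAEs a window with its own end date and never says that the AE window also applies to them. The inclusive default in 7.3 belongs to the partial-date rule and does not choose between windows. The conflict between the two SAP windows does not depend on which amendment is consulted.

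**Conclusion.** The point holds as a defect of definition. Taken as written, the SAE window is shorter than the AE window by 62 days (59 to 65) for every patient with an on-schedule visit, or by max(0, 62 − d) days under the trial-level meaning. This defeats the aim stated in the same section. The possible result is inconsistent classification of SAEs between day 29 and day 90, not a demonstrated loss of events.

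The sizes assume on-schedule EOS visits and, for the trial-level meaning, that the last visit in the trial follows the last dose in the trial. SAE collection stops at 28 days once a patient starts new anti-cancer therapy, so the gap matters only for patients who have not done so. The numbers of patients and events affected are unknown. All the tables are descriptive, so safety counts are at stake and no test result is. The SAP should be corrected before the final tables are run.

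**What to change.** In SAP 7.1, define an SAE as treatment-emergent if it starts or worsens between first dose and the later of 90 days after last dose and EOS, and state whether EOS is the visit or the Protocol 4.7 date.

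In SAP 9.7.3, state that this single flag for serious events is used in all TEAE tables: overall, serious and leading to death. Changing the window alone is not enough. With a trial-level EOS, an SAE on day 200 could enter the serious table while the 90-day AE window kept it out of the overall table. One flag makes the serious table a subset of the overall table in every case.

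The cost is a few sentences and one derived flag. Serious-event counts may rise slightly.
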